11.4.4 Events Not to Be Considered as AEs/SAEs

Medical conditions present at the initial study visit that do not worsen in severity or frequency during the study are defined as Baseline Medical Conditions and are NOT to be considered AEs. Progression of underlying disease is not an AE and therefore not an SAE per se, rather an efficacy endpoint, unless deemed to be causally related to administration of IP. However, if

adverse signs or symptoms occur in association with disease progression then these should be recorded as AEs and reported as SAEs if meeting any seriousness criteria.

11.4.5 Abnormal Laboratory Findings and Other Abnormal Investigational Findings

Abnormal laboratory findings and other abnormal investigational findings (e.g. on an ECG trace) should not be reported as AEs unless they are associated with clinical signs and symptoms, lead to treatment discontinuation, or are considered otherwise medically important by the Investigator. If an abnormality fulfills these criteria, the identified medical condition (e.g. low white blood cell count, increased ALT) must be reported as the AE rather than the abnormal value itself.

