4.4 Dose Rationale

The effect of intermittent schedules of tipifarnib was tested in several phase 1 studies, including a 5-day bid dosing followed by 9-day rest (5-day schedule: ([Zujewski 2000](#)) and two trials investigating a 7-day bid dosing followed by 7-day rest (7-day schedule: ([Lara 2005](#), [Kirschbaum 2011](#))). In the 5-day schedule phase 1 trial in patients with non-hematological malignancies, doses from 25 to 1300 mg bid were explored. No MTD was identified. Dose-limiting toxicity of grade 3 neuropathy was observed in one patient and grade 2 fatigue in 4 of 6 patients treated with 1300 mg bid. Fatigue, that was not dose-limiting, was observed at the prior dose level (800 mg bid). Of note, myelosuppression which was the most common toxicity in the 21-day schedule (45% at 300 mg bid, Tipifarnib Investigator's Brochure 2018), was limited with the 5-day schedule and included a grade 3 neutropenia in a patient with a prior history of myelosuppression treated with 50 mg bid and a grade 2 thrombocytopenia in a patient treated at the 1300 mg bid dose level. No objective responses were noted.

In the first of the weekly schedule studies ([Lara 2005](#)), the starting dose was 300 mg bid with 300 mg dose escalations to a maximum planned dose of 1800 mg bid. Two of 6 patients with non-hematological tumors in dose level 3 (900 mg bid) developed grade 3 fatigue attributable to study drug, and 600 mg bid on alternate weeks was identified as the recommended phase 2 dose. There were no objective responses but 4 out of 21 patients, 3 of whom had NSCLC, remained on

study for at least 1 year with stable disease (12, 13, 16 and 17 months). Five grade 3 events of myelosuppression (out of 21 patients) were described by the authors (doses not indicated) that were not considered dose limiting toxicities (DLTs) and hematological toxicity was described as moderate and manageable.

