11.2 Method and Timing

At each study visit, the subject will be queried on changes in his/her condition. During the reporting period of the study any unfavorable changes in the subject's condition will be recorded as AEs, whether reported by the subject or observed by the Investigator.

Complete, accurate and consistent data on all AEs experienced for the duration of the reporting period (defined below) will be reported on an ongoing basis in the appropriate section of the eCRF. Among these AEs, all SAEs must be additionally documented and reported using the Serious Adverse Event Report Form. It is important that each AE report include a description of the event, its duration (onset and resolution dates, including time when it is important to assess the time of AE onset relative to the recorded treatment administration time), its severity, its relationship with the study treatment, any other potential causal factors, any treatment given or other action taken (including dose modification or discontinuation of the IPs) and its outcome. In addition, serious cases should be identified, and the appropriate seriousness criteria documented. Specific guidance can be found in the eCRF completion and monitoring conventions provided by the Sponsor.

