11.3 Adverse Event Reporting

11.3.1 Procedure for Reporting Adverse Events

The AE reporting period for safety surveillance begins when the subject is included into the study (date of first signature of AIM-HN informed consent) and continues through the study's post-treatment follow-up period, defined as approximately 30 days from the final administration of the study treatment or immediately before initiation of any other anticancer therapy, whichever comes first.

The Investigator is required to grade the severity/intensity of each AE. Investigators will reference the NCI-CTCAE v 5.0. This is a descriptive terminology that can be used for AE reporting. A general grading (severity/intensity) scale is provided at the beginning of the referenced document, and specific event grades are also provided. If a particular AE's severity/intensity is not specifically graded by the guidance document, the Investigator is to revert to the general definitions of Grade 1 through Grade 5 and use his or her best medical judgment.

The 5 general grades are:

- Grade 1: Mild

- Grade 2: Moderate
- Grade 3: Severe or disabling
- Grade 4: Life-threatening
- Grade 5: Death related to AE. Note: Death (Grade 5 as defined by NCI-CTCAE version 5.0) is mainly regarded as an outcome, to be documented as described below.

According to the Sponsor's convention, if a severity/intensity of Grade 4 or 5 is applied to an AE, then the Investigator must also report the event as an SAE as per [Section 11.4.2](#). However, a laboratory abnormality with a severity/intensity of Grade 4, such as low white blood cell count or increased ALT, is considered serious only if the condition meets one of the serious criteria described below.

In the case of death, the primary cause of death (the event leading to death) should be recorded and reported as an SAE. "Fatal" will be recorded as the outcome of this respective event; death will not be recorded as separate event. Only if no cause of death can be reported (e.g., sudden death, unexplained death), the death per se might be reported as an SAE.

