11.4 Definitions

11.4.1 Adverse Events

An AE is any untoward medical occurrence in a patient or clinical investigation subject administered a pharmaceutical product, which does not necessarily have a causal relationship with this treatment. An AE can therefore be any unfavorable and unintended sign (including an abnormal laboratory finding), symptom, or disease temporally associated with the use of a medicinal product, whether or not considered related to the medicinal product. In cases of surgical or diagnostic procedures, the condition/illness leading to such a procedure is considered as the AE rather than the procedure itself. In case of a fatality, the cause of death is considered as the AE, and the death is considered as its outcome.

Relatedness of an AE will be evaluated as follows:

- Not related: Not suspected to be reasonably related to the IPs. AE could not medically (pharmacologically/clinically) be attributed to the IPs under study in this clinical study protocol. A reasonable alternative explanation must be available.

- Related: Suspected to be reasonably related to the IPs. AE could medically (pharmacologically/clinically) be attributed to the IPs under study in this clinical study protocol.

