### 9.8.1 Adverse Events

All summaries of AEs will be based on treatment-emergent AEs (TEAEs) unless otherwise indicated.

TEAE is defined as AE that starts on or after the first dose of the study drug and within 30 days of the last administration of the study drug.

Counting of AEs will be by subject, not by event; subjects will be counted only once within each SOC or PT.

The count and percentage of subjects who report TEAEs will be summarized for AIM-HN safety analysis set as follows:

TEAEs by SOC and PT

TEAEs by PT (Any Grade and Grade  $\geq$  3)

TEAEs by SOC, PT, and maximum NCI-CTCAE grade

Serious TEAEs by SOC and PT

TEAEs related to tipifarnib by PT (Any Grade and Grade  $\geq$  3)

TEAEs related to tipifarnib by SOC, PT, and maximum NCI-CTCAE grade

Serious TEAEs related to tipifarnib by SOC and PT

TEAEs leading to discontinuation of tipifarnib by SOC and PT

TEAEs with an outcome of death by SOC and PT

Non-Serious TEAE experienced by  $\geq$  5% of subjects by PT

For grade summaries, subjects with multiple events within a particular SOC or PT will be counted under the category of their most severe event within that SOC or PT. Events will be sorted by descending frequency by SOC, and by PT within SOC for summaries.

AEs will be listed for individual subjects, including information regarding onset, duration, severity, seriousness, outcome and relationship to study drug.

AEs will not be summarized by Cycle, except for Overall Summary and AEs by SOC and PT for Cycle 1.

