## 9.8.3 Clinical Laboratory Parameters

Clinical laboratory assessments (hematology and clinical serum chemistry) will be summarized descriptively based on observed values at baseline and each post-baseline scheduled visit and change from baseline. All laboratory results (hematology, clinical serum chemistry, urinalysis, and coagulation) will be reflected in listings.

Shift tables for some hematology and chemistry tests will be provided for the maximum post-baseline grade including data from any scheduled and unscheduled visits prior to or on end of treatment visit. These tables will compare the NCI-CTCAE grade for the baseline value relative to each post-baseline time point value for all non-missing post-baseline data. Subjects meeting shift criteria for high values as well as low values during the course of the trial will be summarized for both criteria.

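### Protocol 11.4.5 does not make a dose hold, dose reduction, transfusion or growth factor use a trigger for reporting a laboratory abnormality as an AE, so asymptomatic cytopenias may be under-counted, unevenly by site, in the TEAE tables

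*Protocol*

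**What the plan says.** - **Reporting rule.** Protocol 11.4.5 states that abnormal laboratory and other investigational findings "should not be reported as AEs unless they are associated with clinical signs and symptoms, lead to treatment discontinuation, or are considered otherwise medically important" in the Investigator's view. When one of these conditions is met, the medical condition is entered as the AE, and low white cell count is one of the examples.
- **General definition.** Protocol 11.4.1 is wider: "An AE can therefore be any unfavorable and unintended sign (including an abnormal laboratory finding), symptom, or disease".
- **Action taken.** Protocol 11.2 asks each AE report to include "any treatment given or other action taken (including dose modification or discontinuation of the IPs) and its outcome". Dose modification is thus an attribute of an AE already on the form.
- **Grade 4.** Protocol 11.3.1 makes other Grade 4 events serious by convention, but "a laboratory abnormality with a severity/intensity of Grade 4, such as low white blood cell count or increased ALT, is considered serious only if" a seriousness criterion is met.
- **AE tables.** SAP 9.8.1: "All summaries of AEs will be based on treatment-emergent AEs (TEAEs) unless otherwise indicated". The tables listed include any grade, grade 3 or higher, related, serious and fatal TEAEs. The only one defined by the action taken with the drug is for discontinuation.
- **Outputs outside the AE tables.** Protocol 12.1.2 promises the incidence of grade 3 and 4 neutropenia, thrombocytopenia and anemia, per cycle and overall, with laboratory grades by CTCAE v5.0. It also promises a report of transfusion and growth factor use. SAP 9.8.3: "Shift tables for some hematology and chemistry tests will be provided", using the maximum post-baseline grade, with listings of all laboratory results. SAP 9.4 counts subjects with interruptions and with decreases and summarises why they occurred.

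**The concern.** The three routes into AE reporting leave out the consequences that the protocol itself expects from this drug's laboratory toxicity. Protocol 4.2.3 and 4.3 put hematological events among the most common AEs. The AIM-HN design (6.2.1) handles toxicity by stepwise dose reduction, and 8.1.4 allows transfusions and growth factors for hematological toxicity. An asymptomatic grade 3 or 4 cytopenia that leads to a held or reduced dose, or to a transfusion, has no objective trigger in 11.4.5.

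At stake is how comparable and complete the TEAE rates are. AIM-HN is a single-arm pivotal study in which safety by CTCAE v5.0 is a secondary objective, and no control arm shares the same reporting habit. If sites use the judgement route differently, the tabulated rates partly reflect site practice, and some dose changes summarised under SAP 9.4 will have no matching AE. The primary endpoint is not affected.

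**Working it through.** The plan states no figure on this point, so the check is a trace through the text, followed by one illustration of scale.

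**1. Which consequences make a laboratory abnormality a reportable AE?**

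| Consequence or feature | Trigger in 11.4.5? | Covered elsewhere in the visible text? |
|---|---|---|
| Signs or symptoms | Yes | - |
| Treatment discontinuation | Yes | SAP 9.8.1 has a TEAE table |
| Investigator judges it medically important | Yes | 11.4.2 gives the sense of the term for SAEs |
| Dose interruption | Not named | 11.2, only for an AE already reported |
| Dose reduction | No | 11.2, only for an AE already reported |
| Transfusion or growth factor | No | 11.2 (treatment given), only for an AE already reported |
| CTCAE grade alone | No | 11.3.1 exempts Grade 4 laboratory values from the automatic SAE convention |

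11.4.5 does not say that discontinuation must be permanent, whereas 12.1.2 speaks of permanent discontinuation. A site could therefore read a temporary stop into it. A dose reduction or transfusion would still not be covered.

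**2. Where does an unreported case go?** Take an asymptomatic grade 3 neutropenia followed by a lower dose, which the Investigator does not call medically important. Under 11.4.5 it is not an AE, so it enters none of the SAP 9.8.1 tables. It should still appear in:
- the laboratory-graded hematology summary of protocol 12.1.2;
- the laboratory listings of SAP 9.8.3, and its shift tables if neutrophils are among the tests chosen;
- the dose-decrease summary of SAP 9.4, with a reason.

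**3. Does the SAP carry the protocol outputs?** SAP 9.8 names no grade 3-4 hematology table by cycle and no dedicated transfusion or growth factor summary. SAP 9.5 may show growth factors among all concomitant medications. SAP 9.8.1 limits AE summaries by cycle to Cycle 1. The shift-table tests are not named. The visible items of SAP section 3 do not withdraw the 12.1.2 summaries, but earlier items there are redacted.

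**4. Scale, as illustration only.** Protocol 4.4 reports five grade 3 myelosuppression events among 21 patients in an alternate-week study, doses not indicated. If these were five different patients (assumption):
- rate = 5/21 = 23.8%, exact 95% CI 8.2% to 47.2%;
- in 80 subjects, the protocol's minimum: 80 × 5/21 ≈ 19.

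The documents give no share unreported, *u*. The tabulated rate is 23.8% × (1 − *u*):

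| *u* (assumed) | Rate shown as TEAE | Subjects of 80 |
|---|---|---|
| 0% | 23.8% | 19 |
| 25% | 17.9% | 14 |
| 50% | 11.9% | 10 |
| 75% | 6.0% | 5 |
| 100% | 0% | 0 |

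The range runs from no loss to complete loss, so the documents do not settle the size.

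**The case against.** The strongest reply is that the toxicity is already measured, and measured better, outside the AE tables. Protocol 12.1.2 promises laboratory-graded cytopenia rates that do not depend on what an Investigator chose to report, together with transfusion and growth factor use. SAP 9.8.3 summarises hematology by visit and lists every result, and SAP 9.4 gives a reason for each type of dose change. This stands. A reader might infer that these cytopenias vanish from safety reporting altogether, and the documents do not support that. What remains is that the SAP does not restate the 12.1.2 outputs, and that laboratory tables do not correct the TEAE rates.

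Second, the judgement route is not empty. Protocol 11.4.2 describes important medical events as including those that may need intervention, and names blood dyscrasias as an example. This also stands: under-counting is possible and likely to be uneven, but not certain.

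Third, 11.4.1 says only that a laboratory finding can be an AE, so 11.4.5 can be read as the operating rule beneath a general definition. That is fair. The two sections pull in different directions without flatly contradicting each other.

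Fourth, section 8.1.2 is redacted, and the eCRF conventions cited in 11.2 are not supplied. Either may already require an AE entry for events that change the dose.

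Finally, a reader might take a 25-50% unreported share from the illustration and conclude that 6 to 12 percentage points are lost. The documents do not support that share, and they report events rather than patients. A subject also leaves an overall grade 3 or higher rate only if no other such TEAE occurred.

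**Conclusion.** The concern holds in limited form. As written, 11.4.5 lets asymptomatic cytopenias that lead to dose interruption, dose reduction, transfusion or growth factor support go unreported as AEs unless the Investigator considers them medically important. The any-grade, grade 3 or higher and related TEAE tables may therefore under-count them, and do so differently from site to site. The effect is confined to the TEAE tables, provided that the 12.1.2 laboratory and transfusion summaries are actually produced, which the SAP does not say. Its size cannot be derived from the documents.

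The conclusion assumes that no instruction in the redacted section 8.1.2 or in the eCRF conventions closes the gap. It is a worthwhile, inexpensive improvement to safety reporting and has no bearing on the primary analysis.

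**What to change.** **Protocol 11.4.5.** Extend the triggers to laboratory abnormalities that lead to dose interruption or dose reduction, or that require transfusion, growth factor or other treatment. Keep the three existing triggers. This brings the section into line with 11.4.1. Align the eCRF conventions.

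**SAP.**
- 9.8.1: add tables of TEAEs leading to interruption and of TEAEs leading to reduction.
- 9.8.3: name the hematology tests in the shift tables, at least neutrophils, platelets and hemoglobin.
- 9.8: carry over from protocol 12.1.2 the laboratory-graded grade 3-4 hematology summary, by cycle and overall, and the transfusion and growth factor summary.

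**If AE collection has closed.** SAP section 3 mentions early closure of the study, and a protocol change at that stage would not recover unreported events. Make the SAP changes anyway, and reconcile the dosing-log reasons for interruptions and decreases with the AE data, listing dose changes for laboratory reasons that have no matching AE.

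**Cost.** Protocol and eCRF-guideline wording, a few more tables, more AE entries for sites, and a higher reported TEAE rate. The change affects reporting only and takes no position on any dose or management rule.

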11.5 Adverse Event Follow-up

All subjects will be followed-up for safety through approximately 30 days after treatment discontinuation or until immediately before the administration of another anticancer treatment, whichever occurs first. Additional safety follow-up may be conducted if unresolved toxicity is present at the End of Treatment visit. The IDMB will provide periodic evaluations of safety and other data to ensure subject safety as well as the validity and scientific merit of the study.

12 STATISTICAL CONSIDERATIONS

This section outlines the statistical analysis strategy and procedures for the study. Specific details of the primary and key secondary analyses will be provided in the Statistical Analysis Plan (SAP). The modified Intent -to-Treat analysis will be the primary analysis set for efficacy analyses and the per-protocol analysis set will be used as the secondary population.

12.1 Statistical Methods

12.1.1 Efficacy

For the AIM-HN analyses, the estimate of the ORR will be calculated based on the maximum likelihood estimator (i.e., crude proportion of tipifarnib treated subjects whose best overall response is Complete Response (CR) or Partial Response (PR) by IRF) using the mITT analysis population set. Confirmation of response is required. The estimate of the objective response rate will be accompanied by 2-sided 95% exact binomial confidence interval. Efficacy will also be evaluated among the planned 80 subjects in the per-protocol analysis set, as well as summarized based on Investigator assessment of tumor response. [REDACTED]

[REDACTED]

[figure not shown]
Time to objective response (OR) and duration of objective response (DOR) will be calculated for tipifarnib treated subjects who achieve CR or PR. For such subjects, the time to OR is defined as

number of days from enrollment in AIM-HN until start of PR or CR (whichever occurs first), while duration of objective response is defined as the number of days from the start date of PR or CR (whichever response is achieved first) to the first date that progressive disease is objectively documented. Disease progression will be determined by IRF using RECIST v1.1 but local treatment decisions will be made by the Investigator based on local tumor measurements and other clinical information. The duration of objective response will be right-censored for subjects who achieve CR or PR and meet one of the following conditions: 1) non-protocol anticancer treatment started before documentation of disease progression, 2) death or documented disease progression after more than 1 missed disease assessment visit, or 3) alive and does not have documentation of disease progression before a data analysis cutoff date. The analyses will be performed as determined by the IRF using RECIST v1.1. Additional supportive analyses will be conducted using the investigator assessment.

The time to OR and DOR will be summarized descriptively using the Kaplan-Meier method. The 50th percentile of the Kaplan-Meier distribution will be used to estimate the median response duration and a 95% confidence interval for the median response duration will be computed.

Progression-free survival (PFS) will be defined as the time (in months) from enrollment into AIM-HN to either first observation of progressive disease or occurrence of death due to any cause within 126 days (approximately 2 time intervals for tumor assessments) of either first administration of tipifarnib or the last tumor assessment. In subjects without a progression date or with a death date more than 126 days after the first administration of study drugs or the last tumor assessment, the PFS time should be censored on the date of last tumor assessment or date of first administration of study tipifarnib, whatever occurs last. Progression-free survival analyses should consider tumor assessments after treatment discontinuation or metastatic surgery. Survival will be defined as the time (in months) from enrollment to the occurrence of death due to any cause. Sensitivity analyses for PFS and survival will be performed according to the FDA Guidance for Industry Clinical Trial Endpoints for the Approval of Cancer Drugs and Biologics (May 2007).

Survival and PFS endpoints will be summarized descriptively using the Kaplan-Meier method. The 50th percentile of the Kaplan-Meier distribution will be used to estimate the median PFS and overall survival and 95% confidence intervals for the median response duration will be computed.

[REDACTED]

Descriptive statistics will be primarily used to summarize the demographic data collected in this study. For continuous variables, the number of patients with non-missing data, mean, either the standard error or standard deviation, median, 25th percentile (first quartile), 75th percentile (third quartile), minimum, and maximum will be presented. For discrete data, the frequency and percent distribution will be presented.

Hierarchical testing to adjust for multiplicity will be employed, beginning with the primary objective and working downward until first $p > 0.025$ 1-sided, at which time testing for purposes of firm conclusions will stop.

Sensitivity analyses will be performed to evaluate the robustness of statistical inferences, e.g., to assess the impact of missing data on the conclusions. In addition, a sensitivity analysis will be conducted to evaluate of the impact of the selected VAF cut point on the primary and key secondary analyses, and to determine the VAF cut point which is most predictive of clinical benefit.

[REDACTED]

[REDACTED]

[REDACTED]

